Gadolinium-based MR contrast agents are routinely used in clinical practice, and allergic reactions are infrequently reported. Nineteen adverse events occurred in 28,340 subjects (0.07%) while the rate of serious allergic reactions was much less than 0.01% (Am J Roentgenol 2001;176:1385-1388 and Acad Radiol 1999;6:656-664). We have used the suggested language for clinically performed contrast MRI studies in the consent form and added the possible risk of hypotension. The FDA recently issued an advisory on gadolinium contrast agents used in MRI causing Nephrogenic Systemic Fibrosis or Nephrogenic Fibrosing Dermopathy (NSF/NFD) which apparently can occur in patients with severe renal disease and have given a black box warning regarding their use in patients with GFR<30ml/min. To date, the FDA reports that they have had no reports of NSF in subjects with normal or only mildly impaired renal function. Over 90% of cases have occurred with Omniscan. Below is our contrast sliding scale for MRIs.

Contrast:

- 1. 0.2 mmol/kg (double dose) Gadavist if GFR>=60 ml/min/1.73m2
- 2. 0.1 mmol/kg (single dose) Multihance if GFR between 45-60 ml/min/1.72 m2
- 3. No contrast if GFR<45 ml/min/1.73 m2

Medical personnel are available to administer necessary medical care in the event of allergic reactions.

c. Plan for reporting unanticipated problems or study deviations.

All clinically significant unanticipated problems or study deviations will be reported to the DSMB and the IRB according to The Johns Hopkins Medicine Institutional Review Boards published guidelines. The DSMB will include a cardiologist familiar with the management of patients with acute coronary symptoms, a statistician, and an individual with a background in medical ethics. The DSMB will have access to study drug assignment and will make recommendations to [name] regarding any safety concerns and continuation of the study.

d. Legal risks such as the risks that would be associated with breach of confidentiality.

Once the data are acquired, they will be assigned a code for each subject with identification secured and accessible only to the principal and other investigators, and the research coordinator. Patient clinical information such as copies of clinical studies and imaging reports will be filed in a locked filing cabinet with access under control of [name], the other investigators, and study coordinators. Patient information summarized and/or converted into electronic form (tables, images, etc.) will be identified by the assigned code. We will abide by the Johns Hopkins Institutional policy that all identifiers in images and data acquired under IRB-approved research protocols must be removed if they leave the institution, for example in presentations.

e. Financial risks to the participants.

All study related costs will be paid from research sources, as stated in the consent form.

12. Benefits

a. Description of the probable benefits for the participant and for society.

It is not known whether the enrolled participants will receive any benefits from the study drug. In general, those participating in clinical trials may benefit by receiving closer follow-up and improved access to physicians (the physician investigators) than do those not participating in such studies. If the results regarding the safety and efficacy outcomes demonstrate a favorable effect of evolocumab, their participation would be expected to benefit future NSTEMI and STEMI patients.

13. Payment and Remuneration

a. Detail compensation for participants including possible total compensation, proposed bonus, and any proposed reductions or penalties for not completing the protocol.

For each outpatient study visit study participants will receive \$75. Additionally, study participants will be reimbursed for transportation and parking expenses and given a \$10 meal voucher following procedures requiring prior fasting.

14. Costs

a. Detail costs of study procedure(s) or drug (s) or substance(s) to participants and identify who will pay for them.

There is no cost to the participants related to the study procedures or drugs.

REFERENCES:

- 1. Ferrante, G., et al., *High levels of systemic myeloperoxidase are associated with coronary plaque erosion in patients with acute coronary syndromes: a clinicopathological study.* Circulation, 2010. **122**(24): p. 2505-13.

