2.2 Secondary (for the intervention study group)

The secondary objectives are to compare in the evolocumab and placebo groups:

a. Serial serum markers of inflammation, platelet and endothelial cell function, lipids, and myocardial injury, and left ventricular function which will be collected at pre-randomization, during hospitalization, at hospital discharge and at 25-30 days, 6 months and 12 months follow up. In those who are discharged before day 3, and those who are unwilling or unable to return to the hospital, additional samples may be obtained in the out of hospital setting.

The time points of comparison are pre-randomization, during hospitalization, at hospital discharge, and any obtained in the outpatient setting including the 30 days, 6 months, and 12 months samples.

- i. PCSK-9
- ii. Soluble LOX-1
- iii. IL-6, IL-10, IL-12
- iv. hsCRP
- v. platelet function
- vi. LDL-Cholesterol
- vii. HDL-Cholesterol
- viii. Triglycerides
- ix. Total Cholesterol
- x. Apolipoprotein B
- xi. Lipoprotein (a)
- xii. Troponin
- xiii. Pro-BNP
- xiv. HbA1c
- xv. Insulin
- b. The change between hospitalization and thirty day of:
 - i. PET-FDG assessed myocardial inflammation and vascular inflammation in the most diseased segment of aorta or carotid artery. For this outcome, separate analyses will also be performed in those who did and did not undergo the initial PET scan within 48 hours of study drug administration.
 - ii. Echo assessed regional wall motion in the infarct territory
 - iii. Echo assessed global LV function
 - iv. Echo assessed LV systolic and diastolic volumes

The times of collection will be at early hospitalization and 30 days. The time point of comparison will be at 30 days

c. At thirty days:

- i. Comparison of PET-FDG assessment of myocardial inflammation and vascular inflammation in the evolocumab versus placebo group as described in 2.2. b i
- ii. Echo assessed as described in 2.2. b ii-iv
- iii. Angina class
- iv. New York Heart Association functional class
- v. Serum markers as described in 2.2. a

d. At six months

- i. Angina class
- ii. New York Heart Association functional class
- iii. Echo assessment as described in 2.2. b ii-iv

In a subset of participants: The change between early infarction period and six months assessments of Cardiac MRI-assessed adverse remodeling, e.g. LV function and volumes, infarct size and scar quantification

e. At 12 months

Serum markers as described in 2.2 a

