d. Justification of why participants will not receive routine care or will have current therapy stopped.

All participants will receive routine care and will not have current therapy stopped.

e. Justification for inclusion of a placebo or non-treatment group.

Inclusion of a placebo, comparator group is necessary to best determine the safety and efficacy of evolocumab in NSTEMI and STEMI patients. As noted above, evolocumab is not considered "treatment" for this patient population and hence we do not believe there is a "non-treatment" group, or ethical concern by inclusion of a placebo group.

f. Definition of treatment failure or participant removal criteria.

There is no defined "treatment failure." Outcomes of those randomized to evolocumab or placebo will be collected to determine whether the "treatment" was or was not successful in terms of the safety and efficacy outcomes.

Participants are volunteers and may decline continued participation and if so will be removed from any further study procedures. In addition, those who undergo unanticipated coronary bypass surgery will not undergo the second PET study as cardiopulmonary bypass itself is associated with increased inflammation and therefore would confound interpretation of the inflammatory outcomes. We will gather the lipid outcomes in these individuals.

Early stopping rules:

The study will be stopped early on the recommendation of the Data Safety and Monitoring Committee or if there is any new published information regarding the safety of the study drug or the study procedures.

g. Description of what happens to participants receiving therapy when study ends or if a participant's participation in the study ends prematurely.

Participants will only receive one dose of the study drug on the day of enrollment and thus will not be receiving any study related therapy when the study ends or if the participant's participation in the study ends prematurely.

Study Procedures (for the observation study group)

- a. Blood draws:
 - i. Participants will undergo 4 blood draws of about 3-4 tablespoons each to measure lipoprotein (a) [Lp(a)], cholesterol levels, and thrombotic and inflammatory markers and mediators. The first blood draw will be at the time the participant presents to the hospital, followed by an additional blood draw during the inpatient stay, a blood draw at a 30-day follow-up visit and a final blood draw at a 6 months follow-up visit.

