- b. Obtaining remnant samples from blood draws in the ED:
 - i. After a patient agrees to participate and signs the ICF, we will access the JHH remnant sample repository to obtain remnant blood from the earliest timepoint at hospital presentation. We will work with the JHBMC Pathology Department to locate and retrieve the samples for analysis of the proposed biomarkers.

5. Inclusion/Exclusion Criteria

- **5.1 Inclusion Criteria** (for the intervention study group)
 - a. Age 25 to 90 years.
 - b. Non-ST-elevation and ST elevation myocardial infarction, with compatible symptoms and ECG changes.
 - c. Permission of attending physician.
 - d. Ability to understand the risk, benefits, and alternatives of participation.
 - e. Ability to administer study drug within one week of hospital presentation.

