- 2) Change in vascular inflammation from the FDG-PET scan obtained during the early post-infarct period and the 25-30 day FDG-PET scan in the evolocumab and placebo groups. Vascular inflammation will be assessed in the average of the TBR (target to background) of the MDS (of most diseased segments) of the carotid artery or aorta in the evolocumab vs. placebo groups. The target to blood pool ratio or TBR is the ratio of the mean activity in the vessel to the venous blood pool. [43]
- 3) Change in myocardial inflammation from the FDG-PET scan obtained during the index hospitalization and the thirty-day FDG-PET scan in the evolocumab and placebo groups.
- 4) Difference in the FDG-PET assessment of vascular inflammation in the MDS of carotid artery or aorta in the evolocumab versus placebo groups at 30 days.
- 5) Difference in the FDG-PET assessment of myocardial inflammation at 25-30 days in the evolocumab and placebo groups.
- 5) Serum markers of inflammation and of endothelial and platelet function in the two randomized groups at 25-30 days.
- 6) Change in serum markers of inflammation and of endothelial and platelet function in the two randomized groups from the index hospitalization to 25-30 days.

Secondary (for the observation study group)

1. Change in levels of inflammatory markers and mediators between the initial hospitalization, during hospitalization and 30-day follow-up

Sample Size Considerations (for the intervention study group)

We are providing power considerations for the primary as well as key secondary endpoints (see Tables 1-3).

Primary endpoints:

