Previously published clinically relevant, drug-induced TBR changes are reported in the range of 5%-15%. [44] The power calculations for a 10% and 15% TBR difference based on a sample size of 50 patients per study arm are outlined in Table 3 below. Table 1 uses a 1-sided p-value of 0.05, under the hypothesis that evolocumab will lower inflammation and will not raise it,

consistent with the approach used in the Dal-PLAQUE study. Calculations are performed using non-parametric statistics accounting for the possibility of non-normally distributed TBR data.

Tables 3: Power calculations using a 1-sided p-value, i.e. only assumes that PCSK9 inhibition will lower TBR in the most diseased segment (MDS) and will not raise TBR.

Table 3			Estimated	Detectable
	N in each group	Median (IQR)	Power at	Point
		TBR in STEMI	10% & 15%	Estimate at
		Population at 30	TBR	70% &
		days	Difference	80% Power
Aorta	N = 50	3.2(2.7-4.0)	88%	-8.1%
MDS			99%	-9.1%
Carotid	N = 50	2.5 (2.1 – 3.0)	97%	-6.4%
MDS			99%	-7.2%

The table above shows good to excellent power to demonstrate a difference of 10%, and an excellent power to show a difference of 15% in the primary outcome.

Mean and standard deviations of anticipated TBR in STEMI population at 30-days:

 \triangleright Aorta MDS: 3.3 ± 0.6

 \triangleright Carotid artery MDS: 2.6 ± 0.4

Since the timepoint of study drug administration may vary between participants hospitalized at JHH and Bayview, we will create a co-variable to document the time period between hospitalization and study drug administration and adjust our analysis accordingly.

Sample Size Considerations (for the observation study group)

Analysis of Lp(a) in 37 patients in the placebo group of the intervention study indicates an increase in Lp(a) (median, IQR) from 64 [41,187] to 82 [37,265] nmol/L from that obtained during the hospitalization and at 30 days. We would like to obtain an earlier value and correlate the findings with other inflammatory markers and mediators. Given the findings in the above analysis, we believe results in 100 additional patients would provide an adequate sample size.

a. Early stopping rules.

The DSMB will perform any interim analysis they require to monitor patient safety and provide reports advising continuation of the study.

10. Study Statistics (observation study):

Statistical Approach

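### The reference sample for change in the serum markers is not named and could be post-dose, and no analysis uses the pre-randomization value already collected

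*Protocol*

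**What the plan says.** The secondary list for the intervention group in protocol Section 9 has two serum-marker items. The second of the two items numbered 5 is "Serum markers of inflammation and of endothelial and platelet function in the two randomized groups at 25-30 days". Item 6 is "Change in serum markers of inflammation and of endothelial and platelet function in the two randomized groups from the index hospitalization to 25-30 days". Neither names a test, model, transformation or covariate, and item 6 does not say which in-hospital sample is the start point.

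There are several candidates. Section 2.2 a says the markers are those "which will be collected at pre-randomization, during hospitalization, at hospital discharge and at 25-30 days, 6 months and 12 months follow up". It also treats the pre-randomization sample as a time point of its own: "The time points of comparison are pre-randomization, during hospitalization, at hospital discharge, and any obtained in the outpatient setting".

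On dosing, inclusion criterion 5.1 e requires "Ability to administer study drug within one week of hospital presentation", and Section 4 g states "Participants will only receive one dose of the study drug on the day of enrollment".

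The only covariate in the intervention statistics is at the end of the Section 9 sample-size text: "we will create a co-variable to document the time period between hospitalization and study drug administration and adjust our analysis accordingly". The SAP covers LDL-C and FDG-PET and does not mention the serum markers. For LDL-C, both documents say explicitly that the baseline is pre-randomization. For FDG-PET, the SAP takes the index hospitalization as baseline.

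**The concern.** The dose is given on the day of enrollment, so samples taken later in the stay, and at discharge, can be post-dose. Hypothesis (3) in Section 1 expects better endothelial and platelet markers already at discharge. If a discharge value, or another in-hospital value after the dose, is subtracted from the 30-day value, the early part of the hypothesized effect is subtracted too.

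The label does not settle the matter. For LDL-C, Section 9 says pre-randomization where it means that. For FDG-PET, the index-hospitalization label covers a scan that Section 2.2 b relates to the time of study drug administration, with separate analyses by whether it fell within 48 hours.

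There is also a missed gain. A pre-dose value of each marker is planned, yet no stated analysis uses it as a covariate. And with both level and change listed, and neither said to govern, the two can disagree with no rule for which to report.

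**Working it through.** **Inputs.** From the documents: 50 per arm; two-sided 0.05 (the SAP's level for its secondary endpoint); Lp(a) SDs of 101 at Day 0 and 147 at Day 30 (Section 10, Table 4). Assumed, because the documents do not give them: the correlation r between the pre-randomization and 30-day values (0.2 to 0.7), and the share f of the 30-day effect already present in a post-dose reference. No power figure is stated for these markers, so there is none to reproduce.

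**Bias.** Let the true 30-day effect be δ, with equal SDs at the two times.
- 30-day level: estimates δ, by randomization.
- Change from a pre-randomization value: estimates δ.
- Change from a post-dose value: estimates (1 − f)δ.
- ANCOVA on a post-dose value: estimates (1 − f·r)δ.
- ANCOVA on a pre-randomization value: estimates δ.

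With f = 0.5, change from a post-dose value recovers 50% of the effect. ANCOVA on that same value recovers 1 − 0.5 × 0.3 = 85% (r = 0.3) or 1 − 0.5 × 0.5 = 75% (r = 0.5). A simulation with 50 per arm and a true effect of 0.56 SD agreed: 0.28 for change from the post-dose value, 0.48 and 0.42 for ANCOVA on it, and 0.56 for the three unbiased contrasts.

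**Precision with equal SDs.** In units of the 30-day variance, the level has variance 1, change 2(1 − r), and ANCOVA on the pre-randomization value 1 − r². Power is by normal approximation for an effect of 0.56 SD, which gives the level 80%.

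| r | Change | ANCOVA | Cut vs level | Cut vs change | Power: change / ANCOVA |
|---|---|---|---|---|---|
| 0.2 | 1.60 | 0.96 | 4% | 40% | 60% / 82% |
| 0.3 | 1.40 | 0.91 | 9% | 35% | 66% / 84% |
| 0.5 | 1.00 | 0.75 | 25% | 25% | 80% / 90% |
| 0.7 | 0.60 | 0.51 | 49% | 15% | 95% / 98% |

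If the reference is post-dose with f = 0.5, power for change falls to 22% (r = 0.3) or 29% (r = 0.5).

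**Precision with unequal SDs.** If the baseline SD is k times the 30-day SD, change has variance 1 + k² − 2rk. The Lp(a) SDs give k = 101/147 = 0.687.
- r = 0.3: (1 + 0.472 − 0.412)/0.91 = 1.060/0.91 = 1.16.
- r = 0.5: (1 + 0.472 − 0.687)/0.75 = 0.785/0.75 = 1.05.

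On that ratio, change has only 5-16% more variance than ANCOVA.

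**Detectable difference.** With the t distribution, 50 per arm, two-sided 0.05 and 80% power, it is 0.566 × √variance in 30-day SD units.
- Level: 0.566 × √1 = 0.57.
- ANCOVA: 0.566 × √0.91 = 0.54 (r = 0.3); 0.566 × √0.75 = 0.49 (r = 0.5).

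Against the level, that is a reduction of about 5% (1 − √0.91) to 13% (1 − √0.75).

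**The case against.** The other side has several good points.

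- The documents do not commit to a faulty analysis. A reader might infer that unadjusted tests are planned, because the SAP gives unadjusted tests for FDG-PET. But no test is stated for the serum markers, and Section 9 promises adjustment for time to study drug. This stands: the finding is an undefined reference and an unstated method, not a wrong method.
- Section 2.2 a names the pre-randomization sample, so the investigators may well mean it in item 6. That is possible, and then no contrast is biased. The text does not say so, however.
- A reader might infer that ANCOVA removes the bias. It does not: on a post-dose value it is still biased. The choice of the pre-randomization sample is the cure, and ANCOVA only adds precision.
- A reader might infer a large loss from change scores because Section 3 reports high hs-CRP and IL-6 in acute infarction. That concerns levels, not variance. The only SDs in the documents for a listed marker over this course, those for Lp(a), are smaller at Day 0 than at Day 30. They are for one marker on the raw scale, so they do not settle the others, but they give no support for a large loss.
- The unbiased 30-day level is already an endpoint, and at low r ANCOVA improves on it only slightly. This stands.
- Section 9 reports Lp(a) results from 37 placebo patients, so a change now is a mid-trial change and needs a date and a reason. This also stands, but it bears on how to make the change rather than whether to make it.

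**Conclusion.** The point holds as a gap in specification with a cheap remedy. Item 6 has no defined start point; a post-dose sample fits its wording, and using one would bias the change contrast toward zero by the share f of the effect already present. The size of f is unknown, and the bias touches item 6 only.

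Separately, the planned pre-randomization value is not used for adjustment. In large samples, ANCOVA on it is at least as precise as either listed contrast. How much it gains depends on r, which must be assumed: it is small against the level when r is 0.3 or less and substantial at 0.5 or more. Against change, it depends also on the ratio of SDs and nearly vanishes at the Lp(a) ratio when r is high.

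The documents do not support saying that the marker comparisons as a whole are biased, or that hypothesis (3) fails with them. That hypothesis concerns endothelial and platelet markers only, and the 30-day level comparison is sound. The primary LDL-C analysis is not affected. These are secondary endpoints with no power statement, so this should be put right but is not critical.

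**What to change.** In Section 9, and in a short serum-marker paragraph added to the SAP:

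1. Define the reference for every serum marker as the last sample before randomization, and state that a sample drawn after the dose is never used as baseline.
2. Make the main between-arm analysis of each marker one ANCOVA of the 25-30 day value on arm and the pre-randomization value, with the planned time-to-drug covariate, measured up to the moment of dosing. Use the log scale where the marker is skewed and report the between-arm ratio; otherwise report the difference. Give the 95% CI in either case. Decide the scale marker by marker; platelet function has no assay or scale stated.
3. Keep the 25-30 day level and the change as descriptive summaries.

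No new samples or visits are needed, since the pre-randomization draw is already planned. The cost is a few lines in each document. The amendment should be dated, should precede any comparison of these markers by arm, and should say what placebo-arm data had been seen by then.

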Evolocumab in Patients With Acute MI NCT04082442 7/14/2021

Evolocumab in Patients with Acute Myocardial Infarction (NCT04082442)

Study Statistics

Cover Sheet

Title: Evolocumab in Patients with Acute Myocardial Infarction: A Double-blind, Prospective, Randomized, Placebo-Controlled Study

Study Type: Interventional (Randomized, Double-Blind, Placebo-Controlled)

Population: Patients with acute myocardial infarction receiving high-intensity statin therapy

Sample Size: 100 participants (50 per arm: Evolocumab vs. Placebo)

Primary Outcome: Percent change in LDL-cholesterol (LDL-C) from baseline to 30 days

Key Secondary Outcome: Change in myocardial inflammation measured by FDG-PET (mean Standardized Uptake Value, SUV) from baseline to 30 days

Analysis Population: All randomized participants with evaluable baseline and follow-up data

Primary Endpoint Analysis

Endpoint Definition: Difference in the mean percent change in LDL-C from baseline (prerandomization) to 30 days in the evolocumab and placebo groups.

Statistical Method:

- Mean ± SD LDL-C at baseline and 30 days will be summarized for each group.
- Between-group comparisons will use an independent-samples t-test (two-sample test of means).
- Percent change will be calculated as: ((LDL-C30d LDL-Cbaseline) / LDL-Cbaseline) × 100.
- Two-sided p < 0.05 will indicate statistical significance.
- Results will also be presented as mean differences with 95% confidence intervals.

Power Considerations: Assuming baseline LDL-C \approx 110 mg/dL, 50% reduction with standard statin therapy, and an additional 50% reduction with evolocumab, a sample size of 50 per group provides >99% power (one-sided α = 0.05) to detect a 13.5 mg/dL absolute LDL-C difference.

Secondary Endpoint Analysis

Endpoint Definition: Change in inflammation quantified as mean FDG-PET Standardized Uptake Value (SUV) from baseline (index hospitalization) to 30 days in the evolocumab and placebo groups.

Statistical Method:

- For within-group change: paired t-test or Wilcoxon signed-rank test (if non-normal).
- For between-group comparisons: independent-samples t-test or Mann-Whitney U test.
- Data will be presented as mean ± SD and mean difference (95% CI).
- Significance defined as two-sided p < 0.05.

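### The vascular TBR power in Protocol Table 3 rests on SDs of 0.6 and 0.4, but the IQRs in the same table imply about 0.96 and 0.67; the SAP repeats the power without its one-sided basis

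*Protocol*

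**What the plan says.** Protocol section 9, Sample Size Considerations, Secondary Endpoint, gives power for 10% and 15% differences in TBR of the most diseased segment, with 50 patients per arm. Table 3 lists:

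| Segment | Median (IQR) at 30 days | Power at 10% / 15% | Detectable at 70% / 80% power |
|---|---|---|---|
| Aorta | 3.2 (2.7–4.0) | 88% / 99% | 8.1% / 9.1% |
| Carotid | 2.5 (2.1–3.0) | 97% / 99% | 6.4% / 7.2% |

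The caption gives the basis: "Power calculations using a 1-sided p-value, i.e. only assumes that PCSK9 inhibition will lower TBR". The text adds: "Calculations are performed using non-parametric statistics accounting for the possibility of non-normally distributed TBR data". The conclusion under the table begins: "The table above shows good to excellent power to demonstrate a difference of 10" per cent. Next come means and SDs for the same population and time point: "Aorta MDS: 3.3 ± 0.6" and "Carotid artery MDS: 2.6 ± 0.4".

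The matching endpoint is number 4 in the protocol's secondary list, the comparison at 30 days: "Difference in the FDG-PET assessment of vascular inflammation in the MDS of carotid artery or aorta".

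The SAP's Secondary Endpoint Analysis defines a different quantity, "Change in inflammation quantified as mean FDG-PET Standardized Uptake Value (SUV) from baseline", and sets one rule: "Significance defined as two-sided p < 0.05". Its Power Considerations then restate the TBR power as above 88% to 99% for differences of 10–15% with 50 per group. They give neither the sidedness nor the 30-day time point.

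**The concern.** For a roughly normal variable the IQR is 1.349 SDs wide. SDs of 0.6 and 0.4 therefore correspond to IQR widths of 0.81 and 0.54, but Table 3 shows widths of 1.3 and 0.9. One quantity has been given two spreads that differ by a factor of about 1.6, and power depends directly on which is used.

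The protocol puts published, clinically relevant drug effects on TBR at 5–15%, so 10% is the middle of the range of interest. If TBR shows no difference, a reader relying on the planning statement would not know whether the trial had 88% power or about 50% power to see a 10% effect. The SAP adds a smaller problem: it carries one-sided power figures into a section that tests two-sided.

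**Working it through.** **Inputs.** n = 50 per arm, the medians, IQRs, means and SDs are all from protocol section 9. The one-sided basis is in the Table 3 caption; the 0.05 level is in the paragraph before it, which refers to Table 1. The two-sided 0.05 rule is from the SAP's Secondary Endpoint Analysis.

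**Formula.** For a two-sample t-test the noncentrality is δ = f × base / (SD × √(2/50)) = f × base / (0.2 × SD), with 98 degrees of freedom, where f is the fractional difference. Ranges below use first the median and then the mean as base (aorta 3.2, 3.3; carotid 2.5, 2.6). Mann-Whitney (MW) figures are simulated with 20,000 replicates from lognormal data; that shape is an assumption.

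**Step 1: reproduce Table 3 (one-sided 0.05, mean as base).**
- Aorta, SD 0.6: δ at 10% = 0.33/0.12 = 2.75. Power is 86.1% by t-test and 88% by MW. Detectable differences are 7.9% (70% power) and 9.1% (80% power). Stated: 88%, 8.1%, 9.1%.
- Carotid, SD 0.4: 94.3% by t-test, 95.5% by MW, detectable 7.7% at 80% power. This misses the stated 97% and 7.2%.
- Carotid, SD 0.374 (which rounds to 0.4): δ = 0.26/0.0748 = 3.48. Power is 96.5% by t-test and 97% by MW; detectable 6.3% and 7.2%. Stated: 97%, 6.4%, 7.2%.

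Table 3 therefore follows the small SDs at one-sided 0.05.

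**Step 2: the spread that the IQRs imply.**
- Aorta: (4.0 − 2.7)/1.349 = 0.964.
- Carotid: (3.0 − 2.1)/1.349 = 0.667.
- A lognormal fitted to the medians and IQRs has means 3.34 and 2.59, close to the stated 3.3 and 2.6, but SDs of 0.99 and 0.70.
- A uniform shape with these quartiles gives 0.75 and 0.52.
- The smallest SD possible with these means and quartiles is √(0.25 × (0.6² + 0.7²)) = 0.46 for the aorta and √(0.25 × (0.5² + 0.4²)) = 0.32 for the carotid. The stated SDs are thus possible, but they need tails lighter than uniform.

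**Step 3: power at n = 50 per arm under each spread (t-test).**

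| | Spread | One-sided, 10% | One-sided, 15% | Two-sided, 10% | Two-sided, 15% |
|---|---|---|---|---|---|
| Aorta | 0.6 | 84–86% | 99% | 75–78% | 98% |
| Aorta | 0.964 | 50–52% | 80–82% | 38–40% | 69–72% |
| Carotid | 0.374 | 95–97% | >99% | 91–93% | >99% |
| Carotid | 0.4 | 93–94% | >99% | 87–90% | >99% |
| Carotid | 0.667 | 59–61% | 87–90% | 46–49% | 80–83% |

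MW power at 10% with the IQR spreads is close to these: one-sided about 54% (aorta) and 61% (carotid); two-sided 41–42% and 48%.

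**Step 4: detectable difference at 80% power.** On the table's own one-sided basis, the IQR spreads give 14.6–15.1% (aorta, stated 9.1%) and 12.9–13.4% (carotid, stated 7.2%). Two-sided, they give 16.5–17.0% and 14.5–15.1%. With the smaller SDs, two-sided, the figures are 10.3–10.6% (SD 0.6) and 8.1–8.5% (SD 0.374).

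**A possible cause (inference only).** Upper quartile minus median, divided by 1.349, gives 0.8/1.349 = 0.593 and 0.5/1.349 = 0.371, very close to the SDs behind the table. That is what results if half the IQR is divided by the constant for its full width. If the bracketed LDL-C ranges earlier in section 9 are all IQRs, as Table 1 labels the first, they show a similar pattern: 20/1.349 = 14.8, 15/1.349 = 11.1 and 14/1.349 = 10.4, against Table 2 SDs of 14, 11 and 10. The documents do not state how any of these SDs were obtained.

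**The case against.** The strongest reply is that Table 3 is not miscalculated. It follows from the SDs printed beside it at a disclosed one-sided level, and the protocol allows for non-normal data by using non-parametric methods. The low-power reading holds only if the IQRs are the correct description and the shape is not unusual. That stands: the inconsistency is certain, the loss of power is conditional. But allowing for non-normality does not close the gap, since the usual departures (skew, heavy tails) raise the SD relative to the IQR.

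The smaller SDs could also be residual SDs after baseline adjustment. That would need a baseline to 30-day correlation of about √(1 − (0.6/0.964)²) = 0.78 for the aorta and 0.80 for the carotid. The protocol states no correlation and labels the figures as SDs of 30-day TBR.

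On the SAP, the two-sided rule sits under an endpoint defined as SUV, so it reaches TBR by placement and not by an explicit statement. That also stands and makes the sidedness point secondary.

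Finally, TBR is not the primary or the SAP's key secondary outcome. At a 15% difference, one-sided power stays near 80% or more even with the wider spreads. A 95% confidence interval, if reported for TBR as the SAP does for SUV, would show the precision achieved. These limit the consequence but leave the 10% claim unsupported.

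**Conclusion.** The concern holds. Protocol section 9 gives two spreads for 30-day TBR that are hard to reconcile, and the stated power uses the smaller one. If the IQRs are right and the shape is near normal or lognormal, one-sided power at a 10% difference is about 50–54% for the aorta and 59–61% for the carotid across the two tests, against 88% and 97% stated, and the claim of good to excellent power at 10% fails. The documents do not show which spread is correct.

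Separately, if the SAP's two-sided rule governs TBR, its figure of more than 88% is not met for the aorta at 10% even with the SD of 0.6: power is 75–78% by t-test and about 80% by Mann-Whitney. The damage is mainly to the 10% claim. The sample size is unaffected.

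**What to change.** 1. Go back to the source of the 30-day TBR figures, reconcile the IQRs with the SDs, and state which spread the power calculation uses.
2. State in the SAP the sidedness and the test that apply to TBR. The only rule now in that section is two-sided 0.05, so recompute Table 3 and the SAP sentence on that basis with one named test.
3. Say in the SAP that the TBR figures refer to the between-group comparison at 30 days.
4. Revise the conclusion below Table 3 to match the recomputed power, giving 10% and 15% separately.
5. Until the spread is settled, show both cases by one method. By two-sided t-test at 10% they are: aorta about 38–40% (IQR) or 75–78% (SD); carotid about 46–49% or 87–93%.

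The cost is less favourable figures in Table 3, the sentence below it and the SAP sentence. No extra patients are needed.
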